3.1 Procedures Overview

The present proposal aims to adapt, pilot and examine the credibility, acceptability, adherence and feasibility of the 3RP adapted for chronic pain (p3RP), and the p3RP-DMD, which is the pain specific 3RP integrated with a commercial digital monitoring device (DMD), the Fitbit. This R34 feasibility project will lay the groundwork for a large RCT of the p3RP-DMD vs p3RP vs pHEP attention placebo control, and will help understand whether the DMD Fitbit is

necessary to comprehensively improve function. Consistent with prior theory within a subsequent R01 we will test the hypothesis that the p3RP-DMD will be superior to the p3RP and pHEP in improving and sustaining improvements in

objective, performance based and self-reported physical and emotional function in patients with heterogeneous chronic pain. Using the specific NCCIH R34 mechanism we now follow an iterative design^{82,83} to adapt the general 3RP and refine both the p3RP and the integrated p3RP-DMD interventions to maximize feasibility, acceptability, credibility, recruitment protocol, adherence and measurements for patients with heterogeneous chronic pain. To allow objective measurement of activity in both p3RP and p3RP-DMD groups, we will use Accelerometer DMDs for 1 week at baseline and post-test. The Fitbit DMD will be used to address/reinforce activity consistent with an individualized pacing plan, and to assess daily activity during the program only for those randomized to the p3RP-DMD.

During the RCT phase, participants will be randomized 1:1 to p3RP-DMD or p3RP using block randomization. The study team will be blinded and the program manager, not involved in the study, will be responsible for assigning numbers to each participant. Participants will not know whether they are assigned to the p3RP-DMD intervention or the p3RP control. Rather, they will be informed that they will be randomized to one of 2 physical activity groups, in an effort to identify which one works best in patients with chronic pain. In order to prevent unblinding, participants will be asked to not share information discussed in the group on social media sites (e.g., Facebook groups or internet chat groups) or with other acquaintances for the duration of the study. We will also explain to study participants how sharing of information would potentially negatively impact the validity of study results.

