
Inclusion Criteria	Rationale
Male and female outpatients, age 18 years or older	Population under study
Have nonmalignant chronic pain for more than 3 months	International Association for Study of Pain (IASP) ¹ criteria
Able to perform a 6-minute walk test	Program will involve increase number of steps/outcome measure
Owns a smartphone with Bluetooth 4.0	Necessary for pairing with DMD and storing/downloading data.
Willingness and ability to participate in the 3RP-DMD intervention and to comply with the requirements of the study protocol (including weekly sessions and daily DMD use).	Human Subjects concern, feasibility
Free of concurrent psychotropic or pain medication for at least 2 weeks prior to initiation of treatment, OR stable on current psychotropic or pain medication for a minimum of 6 weeks and willing to maintain a stable dose	Treatment confound
Leads a sedentary lifestyle	Treatment confound
Exclusion Criteria	Rationale
Diagnosed with a medical illness expected to worsen in the next 6 months (e.g., malignancy)	Treatment confound
Serious mental illness or instability for which hospitalization may be likely in the next 6 months	Feasibility, participant safety
Current suicidal ideation reported on self-report	Subject safety
Lifetime history of schizophrenia, bipolar disorder, or other psychotic disorder, current substance abuse or dependence and	Treatment confound
Current substance use disorder, within the past 6 months	Treatment confound
Practice of yoga/meditation, or other mind body techniques that elicit the RR, once per week for 45min or more within the last 3 months or less.	Treatment confound
Regular use of DMD in the last 3 months.	Treatment confound

Engagement in regular intensive physical exercise for >30 min daily.	Treatment confound
Unable to walk without use of assistance (e.g., walker, cane, wheelchair)	Treatment confound
Limitations/restrictions on physical activity due to health conditions	Feasibility, participant safety

Adaptations for the p3RP will follow the same framework without any of the DMD specific adaptations. All adaptations will occur after input from patients through the focus groups.

II. SPECIFIC AIMS

Specific aims for phase I are:

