Aim 1: In the first step our multidisciplinary team will propose modifications to the general 3RP to address the needs of patients with chronic pain reported in the literature, with a focus on improving physical activity and function (see Figure , Table 1). Based on this information, we will develop a semi-structured qualitative interview script.

Hypotheses: NA

Aim 2: In the second step we will use the semi-structured qualitative interview to guide focus groups (30 total) to gather feedback on the intervention components, gauge treatment needs and expectations, as well as barriers and ways to facilitate participation in the intervention and adherence to the use of DMD and 3RP specific practice, among chronic pain patients. Participants will also be given an exit interview to answer questions that they might not feel comfortable discussing during the group setting (e.g., triangulation).

Hypotheses: NA

Specific aims for phase II are:

Aim 3: In the first step, we will pilot the adapted p3RP-DMD and p3RP programs in two initial groups (N=10/group, 20 total) of chronic pain patients and assess preliminary credibility, acceptability, satisfaction of treatment, feasibility (of recruitment and instruments) and adherence to the use of the DMD and to p3RP-specific homework.

Hypotheses: N/A

Aim 4: In the second step, we will conduct a semi-structured comprehensive qualitative exit interview at the end of the groups focused on discussing patients' perception of the rationale for and helpfulness of each individual p3RP specific module, patients' perception of the rationale and helpfulness of using the DMD in increasing physical activity/function, patients' perception of the importance and ease of adherence to DMD and adherence to p3RP specific homework, and patients' burden of questionnaire completion.

Hypotheses: N/A

Specific aims for phase III are:

Aim 5: We will conduct an RCT (N = 80 chronic pain patients, 40/arm, 8 groups total, accounting for 25% attrition) of the newly refined p3RP-DMD versus the newly refined p3RP. We will compare the credibility, acceptability, adherence, satisfaction with treatment, feasibility (of recruitment, refined intervention, study procedures, and instruments) between the two interventions.

Hypotheses: N/A

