Aim 6: By the end of this trial we aim to have two interventions (p3RP-DMD and p3RP) with high credibility, acceptability and feasibility, a recruitment, retention plan and study procedures protocol to ensure minimal random error, and outcome measures sensitive to change.

Hypotheses: N/A

Aim 7: At the end of study enrollment (e.g., no longer recruiting or enrolling participants and only conducting follow-ups with participants and conducting data analysis), we will conduct semi-structured qualitative interviews (12 total) once participants have completed all study procedures (e.g., completing both baseline and post-test questionnaires and wearing the accelerometer at both time points). This interview will be used to inform the future development of the program and to understand ways to better improve physical activity and discuss participants perceptions of the accelerometer.

Hypotheses: N/A

III. SUBJECT SELECTION

Subjects will be adult new patients presenting to Partners-affiliated medical practices (e.g., the Pain Clinic at Massachusetts General Hospital, the Spine Center at Massachusetts General Hospital, Brigham and Women's Hospital Anesthesia and Pain Management Center, and Spaulding Rehabilitation Hospital's outpatient center), and Boston area pain centers and medical practices that treat chronic pain patients. The MGH Center for Pain Medicine sees approximately 15,000 patient visits yearly. The main diagnoses are: chronic low back pain and fibromyalgia. Inclusion and exclusion criteria were selected following guidelines for psychosocial treatment development 82-83 (see Table 1. Above).

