Participants will be recruited among patients with heterogeneous chronic pain who present to Partners-affiliated medical practices (e.g., the Pain Clinic at Massachusetts General Hospital, the Spine Center at Massachusetts General Hospital, Brigham and Women's Hospital Anesthesia and Pain Management Center, and Spaulding Rehabilitation Hospital's outpatient center), Boston area pain centers and medical practices that treat chronic pain patients, and meet study criteria. Participants may also hear about the study from Partners Rally, from chronic pain groups online, or recruitment flyers with tear-off research coordinator contact information that will be posted in the hospital and around referral sites. We will also post to our Twitter page, with the following content: "Can increased physical activity with or without the help of a Fitbit help with chronic pain? IBHCRP's GetActive! study is looking to find out! To learn more or get involved, click [here](#):" with a link to our study on Rally or an attachment of the flyer. All patients within the clinic meet with a medical provider for a medical evaluation as part of usual care, which also includes a urine toxicology pain profile for patients on controlled substances and review of the MA Prescription Monitoring Program.

Recruitment will also occur through the Research Patient Database Registry (RPDR). The RPDR is a centralized clinical data registry that gathers data from various hospital legacy systems and stores it in one place. Researchers access this data using the RPDR online Query Tool. They may query the RPDR data for aggregate totals and, with proper IRB approval, obtain medical record data. The RPDR ensures the security of patient information by controlling and auditing the distribution of patient data within the guidelines of the IRB and with the use of several built-in, automated security measures. To identify potentially eligible patients:

- 1.) An RPDR query will be performed to identify those patients with chronic pain diagnoses. Study staff will review the medical record to confirm potential participant eligibility and to identify their linkage to an MGH primary care physician. Access to patients' medical records will be restricted to this pre-enrollment recruitment phase.
- 2.) Study staff then will obtain permission for initial contact from each potentially eligible patient's PCP by having providers review letters and discard ones that they do not approve.

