During enrollment, participants have the option to consent to receiving reminders in the form of phone calls, text messages, or email over the course of the intervention, depending on personal preference. Between-session contact will be used with the goal of increasing treatment adherence and engagement. Participants may opt-out of the text message contact option at any point.

After enrollment, participants will be assigned to one of the two intervention groups using a randomized block design to ensure that equal numbers of patients are split into the p3RP-DMD and p3RP groups. To prevent participant unblinding, participants will be asked not to share specific information discussed in the group (e.g., skills learned, topics discussed) on social media sites (e.g., Facebook groups or internet chat groups) or with other acquaintances for the duration of the study. The groups will be conducted in person at MGH by trained study therapists over 12 weeks and include 10 active intervention sessions. Each session will last approximately 90 minutes. Participants will also be asked to answer follow-up assessment questionnaires 3 months following program completion. These questionnaires will be administered over the phone for 30-45 minutes.

Participants will complete demographics assessments at baseline, in addition to psychological/behavioral assessments and a 6-minute walk test at both baseline and post-test timepoints. Participants in the p3RP-DMD group will pair their Fitbit DMD to a smartphone with Bluetooth, and the Fitbit will inform an individualized quota-based behavioral plan to improve both adherence and efficacy. All participants will also wear an accelerometer for 7 days before the first treatment session (baseline) and for 7 days after the final treatment session (post-test). After each assessment week, participants will return the accelerometers in addition to a wear time log.

The following measures will be administered at all timepoints unless otherwise stated. Questionnaires at 3-month follow-up will be administered over the phone.

Demographics – *baseline only*

Credibility and Expectancy Questionnaire (CEQ) – *baseline only*

Pittsburgh Sleep Quality Index (PSQI)

PROMIS Physical Function SF

Physical Activity Scale for Individuals with Physical Disabilities (PASIPD)

WHO Disability Assessment Scale (WHODAS) 2.0

Numerical Rating Scale for Pain (NRS)

Pain Resilience Scale (PRS)

PROMIS Anxiety SF

PROMIS Depression SF

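### Phase III measures credibility once, at baseline, with its order relative to assignment unstated: a weak basis for Aim 5's comparison of the two arms

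*Combined protocol and SAP*

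**What the plan says.** - **Aim 5 (Section II)** sets up the trial: "We will conduct an RCT (N = 80 chronic pain patients, 40/arm, 8 groups total, accounting for 25% attrition". Of the two interventions it says: "We will compare the credibility, acceptability, adherence, satisfaction with treatment, feasibility". Credibility is named first. The hypothesis entry is N/A.
- **Aim 6 (Section II)** wants to finish with "two interventions (p3RP-DMD and p3RP) with high credibility, acceptability and feasibility".
- **Section V, Phase III, measures list** gives one credibility instrument: "Credibility and Expectancy Questionnaire (CEQ) – *baseline only". The list's default is every timepoint unless marked otherwise, so this entry excludes post-test and the 3-month follow-up.
- **Section V, Phase III** describes block-randomized assignment after enrollment, then the baseline assessments and Fitbit pairing. It does not state their order in time. The one timed definition of baseline belongs to the accelerometer week, which precedes the first treatment session.
- **Section 3.1** on blinding: "Participants will not know whether they are assigned to the p3RP-DMD intervention or the p3RP control". It continues: "Rather, they will be informed that they will be randomized to one of 2 physical activity groups".
- **Eligibility and recruitment text** reveals more. One inclusion criterion reads "Willingness and ability to participate in the 3RP-DMD intervention", and the social media post in Section III asks "Can increased physical activity with or without the help of a Fitbit help with chronic pain". Both arms see this material.

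**The concern.** Credibility is a judgement about a particular program, so comparing two programs needs ratings from people who know something of the one they are to receive. A single score before the first session, under a plan that withholds the arm, may hold little or no such information. Similar scores could then be read as evidence that the arms are equally credible when they show only that both rated the same description.

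Nothing else listed for Phase III fills the gap. The CSQ-3 measures satisfaction and the PGIC measures perceived change. The 12 exit interviews concern program development, physical activity and the accelerometer. None is described as covering credibility, and Section VI plans no quantitative analysis of it.

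**Working it through.** The plan states no figure for credibility, so there is none to reproduce. The first step is reasoning from the schedule; the second sizes the proposed remedy.

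**Step 1. What a baseline CEQ can show**

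| Order of events | What participants rate | What the between-arm difference can show |
|---|---|---|
| CEQ before any arm-specific information | The same description in both arms | Expected value 0 by randomization; any observed difference is chance |
| CEQ after assignment, before the first session | Whatever they have learned or inferred about their arm, which Section 3.1 tries to withhold | Possibly the idea of the arm; not the delivered program |

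The Fitbit disclosure in the recruitment and eligibility text does not change the first row, because it reaches both arms alike. A larger sample would not help either, because the limitation is one of timing.

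**Step 2. Precision of a repeat CEQ after an early session**

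Inputs from Aim 5: 40 per arm and 8 groups. Assumptions: four groups per arm, an intraclass correlation (ICC) of 0.01 to 0.10, and 30 per arm as an illustrative low case. The 30 is 40 × 0.75, but the plan does not tie its 25% attrition to an early session.

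Formulas, in SD units:
- group size m = n/4
- design effect DEFF = 1 + (m − 1) × ICC
- degrees of freedom = 8 − 2 = 6, so t(0.975) = 2.447
- 95% half-width = 2.447 × √(2 × DEFF / n)

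| n per arm | m | ICC | DEFF | Half-width (SD) |
|---|---|---|---|---|
| 40 | 10 | 0.01 | 1.09 | 0.571 |
| 40 | 10 | 0.05 | 1.45 | 0.659 |
| 40 | 10 | 0.10 | 1.90 | 0.754 |
| 30 | 7.5 | 0.01 | 1.065 | 0.652 |
| 30 | 7.5 | 0.05 | 1.325 | 0.727 |
| 30 | 7.5 | 0.10 | 1.65 | 0.812 |

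Example, first row: 2.447 × √(2 × 1.09 / 40) = 2.447 × 0.2335 = 0.571.

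Ignoring the groups and using 1.96 would give 1.96 × √(2/40) = 0.44 SD at 40 per arm and 1.96 × √(2/30) = 0.51 SD at 30, which is too optimistic. In a simulation of 8 groups of 10 (20,000 trials at each of ICC 0.01, 0.05 and 0.10), intervals on group means with the 6-df t reference covered 0.948 to 0.951. With 1.96 they covered 0.901 to 0.905.

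**The case against.** The strongest reply is that the defect is certain under only one ordering. Section V narrates assignment before the baseline assessments. If the CEQ follows assignment and participants have learned or guessed their arm, it gives a pre-treatment credibility rating by arm. Aim 5 does not say that credibility must be rated after exposure. This is fair, and it is why the conclusion is conditional. It does not rescue the schedule: narrative order is not a stated sequence, and Section 3.1 aims to keep the arm unknown.

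Other points on that side:

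- *Phase II also addresses credibility.* It has credibility questionnaires and an exit interview that asks about confidence in the treatment and therapist. That supports Aim 6. It cannot supply Aim 5's randomized comparison, because pilot participants chose their program until one group was full and the programs were refined afterwards.
- *Baseline-only timing may be deliberate.* The Phase II text says assessment length and timing would be refined, so burden may explain the choice. That would not make an uninformed rating separate the arms.
- *The consent form may say more.* It was not available for this review. It could change what participants know at baseline, but Section V would still lack the order of events.
- *The remedy is imprecise and depends on attendance.* Both are true. A repeat rating would resolve only large differences and could include therapist and group effects.
- *The stakes are low.* Also true: Aim 5 has no hypothesis, and the stated feasibility criterion in Section IX is session completion.

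**Conclusion.** The concern holds, as a minor one. The Phase III schedule is a poor basis for comparing credibility between the arms. The expected difference is exactly 0 if the CEQ precedes arm-specific information. If it follows assignment, the size cannot be stated from the documents. In neither case does a listed Phase III measure rate credibility after exposure to the program. For Aim 6 the loss is partial, because Phase II contributes credibility data.

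Calling the Aim 5 comparison descriptive is an inference from the N/A hypothesis and the absence of a planned test; the plan does not use that word. The core conclusion rests on no numerical assumption. The ICC range, the four-per-arm split and the 30 per arm bear only on the precision of the remedy.

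**What to change.** 1. State in Section V when the baseline CEQ is completed relative to assignment and Fitbit pairing. Keep it as an expectancy measure.
2. Repeat the CEQ in both arms after the same early session: the first by which the manual has introduced the program rationale and, in p3RP-DMD, the Fitbit.
3. Report each arm's mean and the between-arm difference with a 95% confidence interval that allows for treatment group, using a t reference on about 6 degrees of freedom for 8 groups.
4. Present the result as a description for Aim 5, and as one source beside the Phase II credibility data for Aim 6. Make no claim of equal credibility from it.
5. Count by arm the participants who never attend and so have no second score.

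The cost is one short questionnaire at a session participants already attend, plus an edit to the schedule. Step 1 alone costs nothing and is needed to interpret the existing score. Keeping the baseline CEQ also guards against the therapist and group effects that an early-session rating may carry.

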2.1. Conceptual model: Our conceptual model of adaptation of the general 3RP¹⁰ follows recommendations from IMMPACT and combines key concepts of ICF with key features of relevance to patients with heterogeneous chronic pain that specifically target improved physical activity/function, and recommendations of multimodal programs to improve outcomes in chronic pain clinical trials⁷⁰. We used a comprehensive conceptualization of physical function that includes patient reported outcomes (e.g., patient's perception of engagement in physical activity and activities of daily living), performance based function (e.g., a more objective test of walking ability) and objective function (in vivo assessment of number of steps). This comprehensive conceptualization is important because it provides data on the impact of pain and treatment effects beyond symptom reduction alone, a primary concern depicted by patient focus groups and surveys³². Our model is based on the guiding hypotheses that the synergistic association between the evidence based skills of the 3RP adapted for the needs of patients with chronic pain, and DMD is the most efficient and effective way to improve emotional function as well as ALL aspects of physical function depicted above, which have been shown as independent in prior research⁸. Adaptations of the multimodal general 3RP will be done consistent with theoretical models of the fear- avoidance model of pain³⁴, cognitive model of pain⁶, acceptance and commitment therapy⁷⁶, mindfulness⁷⁷, and positive psychology⁷⁸, to help patients engage in activities that are meaningful and mapped to each individual's level of functioning and life circumstance through the use of quota based pacing with in vivo reinforcement facilitated by the DMD (Figure 1). As depicted, we propose that the interrelation among pain specific RR elicitation techniques, pain and activity awareness and adaptive strategy including increased activity will lead to decreased reactivity to pain, increased activity and promote awareness and calm during activities, even when these are painful. The built in, live reinforcement of activity through the DMD and pairing of physical activity with activities of daily living depicted by patients as important are conceptualized as key factors in improving outcomes will maintain motivation and help participants stay accountable for meeting specific physical activity goals. The p3RP and Fitbit DMD are conceptualized as acting synergistically. p3RP acts by directly addressing habitual negative affective reactions to pain and negative pain thoughts by focusing on accepting and learning to tolerate pain sensations (including during increased activity) by using various RR strategies, positive psychology concepts and adaptive thinking¹⁰, while Fitbit DMDs, based on operant approaches previously depicted as promising in this population, directly increased activity through "quota-based" non "pain contingent" activity and direct feedback on number of steps achieved^{79,80}. In our conceptualization the DMD is necessary in order to bypass barriers to physical activity, maintain motivation and reinforce activity in real time.

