
In sum, both the adapted 3RP and the operant based Fitbit DMD approach improve physical and emotional function by focusing on increasing activity regardless of pain^{81,19,10}, and their interaction is hypothesized to further improve outcomes. Proposed changes to the general 3RP are depicted in **CAPS IN RED**. The DMD will give direct reinforcement and monitoring of activity, while the 3RP will aid with pain specific coping skills that act as deterrents from activity in chronic pain, such as nonadaptive cognitions, fear of pain, hypervigilence to pain sensations, among others. Adaptations for the pain specific 3RP (p3RP) will be identical but will not target adherence to the DMD including meeting daily step goals. The model depicted in the figure below specifies that the p3RP and DMD (e.g., p3RP-DMD) will interact and improve physical function both directly and indirectly through improved coping, decreased pain catastrophizing and decreased fear of pain.

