3.2. The 3RP. The novel 8-week group-based general 3RP¹⁰ has been developed by a team led by [name] aided by [name], and will be further adapted for patients with heterogeneous chronic pain including increased physical activity. Drs. [name] and [name] have extensive experience adapting and delivering the 3RP to a variety of populations (see preliminary data). [name] published the first and only RCT¹⁶ of the 3RP adapted for patients with neurofibromatosis (NF; 3RP-NF) and found excellent feasibility and acceptability, as well as level 2 evidence of improvement in quality of life in those randomized to 3RP-NF versus those who attended the attention placebo control HEP-NF; improvements maintained at 6 months follow-up. The 3RP model and proposed adaptations for the needs of patients with chronic pain, including integration of DMD are depicted in Figure . A description of each of the 8 general 3RP group sessions as well as adaptations for proposed for the p3RP-DMD are depicted in Table 1. Adaptations for the pain specific p3RP will be identical but will not include DMD integration adaptations. The 3RP introduces and reinforces new skills through didactics, in-session activities, discussions, and daily home practice assignments. Homework involved setting SMART goals, recording type and amount of daily RR practice, and recording daily 1-3 appreciations. Each session begins with the practice of a new exercise to elicit the RR. The relaxation method is then coordinated with the remaining session content. For instance, the clinician may introduce imagery of a peaceful place as a relaxation method, and then transition to didactics and exercises that focus on skills for building a positive perspective. The main proposed adaptation is the focus on pain as a stressor, rather than on general stress, and uses skills to directly target increased physical activity. General adaptations will include: 1) setting weekly SMART goals specific to quota based pacing to increase activity, individualized to each patient based on baseline or subsequent activity level in the previous block, and instruction on how to pair these with feedback from Fitbit (in the p3RP-DMD only); 2) modification of all RR exercises to address habituation to pain, mindfulness when experiencing pain; 3) employment of RR during exercise to cope with pain and increase enjoyment; 4) pairing exercise with activities of daily living that are important to participants, and link these within the SMART goals; 5) education information of the benefits of exercise, decrease sedentary time, and healthy patterns of activity in chronic pain through non pain contingent pacing; 6) pain specific adaptations of all skills (pain acceptance, restructuring of nonadaptive pain thoughts, etc); 7) specific Fitbit instructions (charging, downloading, using feedback, etc).

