Patients will be informed that there are no foreseeable physical risks from this research study. They will be informed that in the unlikely situation that they might feel uncomfortable with the topic of discussing within the group, they can alert the group leader who will provide help, as needed.

As Vidyo is HIPAA approved and secure, there are no risks associated with its use. However, participants will be asked to ensure that they are in a private room during the group sessions, to protect their privacy and that of group members. As with any group studies, there may be confidentiality issues, but we will discuss the importance of maintaining confidentiality at the beginning of each group.

VIII. POTENTIAL BENEFITS

Patients will be informed that there may be no direct benefit from participating in this research study. Some patients may become more physically active, more resilient, better able to cope with pain and stress, and experience a better quality of life.

In the future, knowledge from this research may benefit others by providing information on how to better mind body interventions for patients with chronic pain.

IX. MONITORING AND QUALITY ASSURANCE

Phase I: The focus groups will be conducted uniformly using a semi structured interview script that will be finalized during the first few months of the study. The Principal Investigator will be responsible for ensuring compliance with IRB procedures.

Phase II: Study therapists will have weekly team meetings and clinical supervision. Study staff will follow the patient manuals for each group and assure that all items on all questionnaires have been addressed. Once completed, data will be checked for out of range values using frequency distributions prior to analyzing the data. The Principal Investigator will be responsible for ensuring compliance with IRB procedures.

Phase III: Feasibility will be assessed as depicted in the prior section. We will calculate the proportion of patients who complete at least 6 of the 8-planned treatment sessions (75%), along with the 95% confidence interval (CI) around this discontinuation rate. Treatments are considered feasible if over 70% of participants complete at least 6 treatment sessions.

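### Section VII's study-wide statement of no physical risk is incomplete for Phases II and III, where the protocol itself plans for pain during increased activity

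*Combined protocol and SAP*

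**What the plan says.** Section VII (Risks and Discomforts) sets one rule for the whole study: "Patients will be informed that there are no foreseeable physical risks from this research study". Apart from that it deals with unease about a discussion topic, privacy during video sessions and confidentiality within the group. Nothing limits the sentence to a phase.

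Other sections describe what Phases II and III involve:

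- Section 2.1 (Conceptual model) expects the programme to "promote awareness and calm during activities, even when these are painful". Its closing summary says that "both the adapted 3RP and the operant based Fitbit DMD approach improve physical and emotional function by focusing on increasing activity regardless of pain". It also describes p3RP itself as teaching people to tolerate pain, including while they become more active.
- Section 3.2 lists among the general programme adaptations "employment of RR during exercise to cope with pain and increase enjoyment". The same list includes "setting weekly SMART goals specific to quota based pacing to increase activity, individualized to each patient based on baseline or subsequent activity level".
- The eligibility table requires a sedentary lifestyle and the ability to do a 6-minute walk test. It excludes people who cannot walk unaided and people whose health restricts their activity; the reason given for the latter includes participant safety.
- Section V, Phase III, schedules a 6-minute walk test at baseline and post-test. Its measures include a numerical pain rating (NRS) and a global impression of change (PGIC), but no item on falls, injuries or flares.
- Section IX, for Phase III, covers session completion, adherence to the manual and device wear.

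**The concern.** The sentence fits Phase I, which is a focus group and a written exit interview. It fits Phases II and III poorly, because both arms there aim to raise activity in people with chronic pain. If staff follow Section VII as written, participants in those phases are told that nothing physical can be foreseen, while the programme prepares them to cope with pain as they exercise.

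A second and lesser matter follows. This study is meant to prepare a large randomised trial. As the document stands, it would reach that point without a planned count, by arm or overall, of falls, injuries or activity-related flares.

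**Working it through.** The plan states no figure on this point, so the main check is textual.

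**1. Scope of the sentence.** Section VII has no subheadings by phase and no qualifier. It therefore governs Phases II and III as well as Phase I.

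**2. The texts side by side.**

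- Section VII: no physical risk is foreseen, and no physical discomfort is listed, although the section is headed Risks and Discomforts.
- Section 2.1: activities may be painful, and activity is increased whatever the pain.
- Section 3.2: coping with pain during exercise is a listed programme component. This is content to be delivered, not only theory.
- Eligibility table: activity restriction is screened out partly on safety grounds, so the matter was considered in advance.
- Section V, Phase III: two walk tests are study procedures.

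Individualised goals and the entry criteria lower the risk. They also show that physical effects were thought about, so they belong in the risk section as mitigation and do not justify leaving it silent.

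**3. How many participants the rule covers.** Aim 5 gives 80 in Phase III. Aim 3 gives 20 in Phase II (two groups of 10), whereas Section V, Phase II, gives 30.

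- 80 + 20 = 100
- 80 + 30 = 110

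**4. Is there a planned harms count?** Sections I to IX were read for one.

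- NRS and PGIC are scores at scheduled assessments. They could show sustained worsening but do not count events.
- The sentence on compliance with IRB procedures in Section IX appears for Phases I and II and is not repeated for Phase III. It does not itself plan a count.
- The Phase III exit interviews reach 12 / 80 = 15% of participants, all of whom completed the study measures. Someone who left because of pain or injury is outside that route.

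No systematic Phase III count is planned in this document.

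**5. What a count could support.** With zero events among n people, the two-sided exact (Clopper-Pearson) 95% upper limit is 1 − 0.025^(1/n).

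- n = 40 (one full arm): 1 − 0.025^(1/40) = 0.088, or 8.8%.
- n = 30 (one arm after the 25% attrition in Aim 5, 40 × 0.75): 1 − 0.025^(1/30) = 0.116, or 11.6%.

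These limits describe the precision of the proposed items. They do not measure harm from the present text, and the documents give no event rate.

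**The case against.** The best case for the sponsor is that Section VII denies physical risk, while Sections 2.1 and 3.2 speak of pain in people who must already have had it for more than 3 months. Coping with existing pain while active is the rationale of the treatment, not a forecast of harm, and the heading of Section 1.4 speaks of raising activity safely. An exclusion made on safety grounds can also be read as removing the risk for those who enter. Much of this stands, and it limits the claim to an incomplete statement. It does not rescue the sentence: a section on risks and discomforts that mentions no physical discomfort is incomplete when the programme plans for pain during activity that the study itself asks for.

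The sedentary-entry criterion is weak support. Section V plans 6 of the 12 Phase III exit interviews with people who were not sedentary at baseline, so the point does not rely on it.

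On the count, Aim 5 does not list harms as an outcome, and no arm lacks an activity goal, so totals would mix background flares with programme effects. That is a fair reason to treat the count as an optional improvement.

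**Conclusion.** The risk and discomfort statement in Section VII is incomplete for Phases II and III, affecting 100 to 110 intervention participants, and should be reconciled with the rest of the protocol. This rests on the protocol text alone.

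A reader might infer three stronger things that the documents do not support:

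- **That the protocol foresees injury or falls.** No section predicts either, and much of the pain it expects is pre-existing.
- **That participants were in fact misinformed.** The consent form is not in the file and may already say more. The fault shown is in the protocol's rule.
- **That Phase III would produce no safety information at all.** NRS, PGIC, exit interviews and any reports under IRB procedures could reveal problems. What can be said is that this document plans no systematic count.

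The missing count is secondary: cheap to add and useful for planning the larger trial, but descriptive only.

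**What to change.** **Main change.** Reconcile Section VII with Sections 2.1 and 3.2, the eligibility table and the Phase III procedures. Limit the present sentence to Phase I. For Phases II and III, state the foreseeable physical discomforts and risks of increased activity, and for Phase III those of the walk tests. Set them beside the mitigation already in the plan: individualised goals, ability to do the walk test, and exclusion of people who need walking assistance or have activity restrictions. The cost is a wording amendment, plus the consent form if it repeats the sentence.

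**Secondary improvement, Phase III.** Add three short items, worded identically in both arms and with a stated recall period: any fall, any injury, any temporary worsening of pain with activity. Ask them at baseline, to give a pre-programme reference, then at post-test and at the 3-month call, and attempt them when someone withdraws. Report each item by arm and overall with exact 95% intervals and the number not answering, without a test.

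The cost is three extra items at assessments that already take place, and a contact attempt for about 20 expected withdrawals (80 × 0.25). Questionnaires become slightly longer, minor events will be under-recalled, and some people who leave will not be reached.
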